### **13.2 For secondary analyses:**

- In the PS-matched cohort from Section 9, calculate the HR for each outcome for liraglutide versus DPP4i patients using a Cox proportional hazards model.
- In both pre-matched cohorts, perform asymmetrical trimming to remove patients with PS values below the 2.5th percentile of treated patients and above the 97.5th percentile of untreated patients. In the trimmed cohort, calculate the HR for canagliflozin versus referent patients using a Cox proportional hazards model, adjusting for deciles of the PS.

## **14. Requested Results**

#### 14.1 Results from primary and secondary analyses:

Separately for each endpoint and each comparator group:

Analysis	No. exposed events	No. referent events	Exposed rate	Referent rate	HR (95% CI)
Crude					
Primary analysis					
Analysis 2					
...					

HR, Hazard Ratio; CI, Confidence Interval.

## Appendix A

#	LEADER trial definitions	Implementation in routine care	Please see the following Google Drive for further details or any missing information: https://drive.google.com/drive/folders/1WD618wrvwYiFaXflTcuK-VCnb6b-g?usp=sharing		
	Trial details- Secondary indication, 4a-unintended superiority with label change		ICD-10 codes are not listed in this document because of excel cell size limitations and excessive number of ICD-10 codes. Full ICD-10 code lists will be available in the above Google Drive Folder (link above). ICD-9 to ICD-10 code conversions were completed using a SAS macro that implements forward/ backward mapping based on the CMS ICD-9 to ICD-10 mapping: https://www.ncbi.nlm.nih.gov/pmc/articles/PMC3037033/		
	EXPOSURE vs. COMPARISON		References/Rationale	Color coding	
	Liraglutide versus placebo	Liraglutide vs. DPP4i or 2nd generation sulfonylurea		Criteria	
	PRIMARY OUTCOME			Adequate mapping in claims	
	
The primary composite outcome in the time-to-event analysis was the first occurrence of death from cardiovascular causes, nonfatal myocardial infarction, or nonfatal stroke. HR = 0.87 (95% CI 0.78-0.97)
		
Measured 1 days after drug initiation in diagnosis position specified below and inpatient care setting: Inpatient mortality/MI/Stroke –
 
For MI Any diagnosis position in inpatient care setting ICD-9 Dx 410.X (acute myocardial infarction) excluding 410.x2 (subsequent episode of care), as the principal (primary) or the next (secondary) diagnosis
 
For stroke Primary diagnosis position in inpatient care setting ICD-9 discharge diagnosis: 430.xx Subarachnoid hemorrhage (SAH) 431.xx Intracerebral hemorrhage (ICH) 433.x1 Occlusion and stenosis of precerebral arteries with cerebral infarction 434.xx (excluding 434.x0) Occlusion and stenosis of cerebral arteries with cerebral infarction 436.x Acute, but ill-defined cerebrovascular events
 
Mortality- See Mortality Sheet.
	
For MI: → PPV 94% in Medicare claims data [Kiyota Y, Schneeweiss S, Glynn RJ, Cannuscio CC, Avorn J, Solomon DH. Accuracy of Medicare claims-based diagnosis of acute myocardial infarction: estimating positive predictive value on the basis of review of hospital records. American heart journal 2004;148:99-104.] → PPV 88.4% in commercially-insured population [Wahl PM, Rodgers K, Schneeweiss S, et al. Validation of claims-based diagnostic and procedure codes for cardiovascular and gastrointestinal serious adverse events in a commercially-insured population. Pharmacoepidemiology and Drug Safety 2010;19:596-603.]
 
For stroke: PPV of 85% or higher for ischemic stroke PPV ranging from 80% to 98% for hemorrhagic stroke → [Andrade SE, Harrold LR, Tjia J, et al. A systematic review of validated methods for identifying cerebrovascular accident or transient ischemic attack using administrative data. Pharmacoepidemiology and Drug Safety 2012;21 Suppl 1:100-28.] → [Tirschwell DL, Longstreth WT, Jr. Validating administrative data in stroke research. Stroke: a journal of cerebral circulation 2002;33:2465-70.] → [Rounie CL, Mitchel E, Gideon PS, Varas-Lorenzo C, Castellsague J, Griffin MR. Validation of ICD-9 codes with a high positive predictive value for incident strokes resulting in hospitalization using Medicaid health data. Pharmacoepidemiology and drug safety 2008;17:20-6.]
	Intermediate mapping in claims

## Appendix A

3a	
 
o Prior coronary, carotid or peripheral arterial revascularization
 
o >50% stenosis of coronary, carotid, or lower extremity arteries
 
o History of symptomatic CHD documented by positive exercise stress test or any cardiac imaging or unstable angina with ECG changes
 
o Asymptomatic cardiac ischemia documented by positive nuclear imaging test, exercise test or dobutamine stress echo
 
	
Measured 180 days prior to drug initiation in any diagnosis position and care setting as defined below:
 
Coronary revascularization (PTCA, stenting, CABG)
 
PTCA:
 
Inpatient CPT-4: 92973, 92982, 92984, 92995, 92996, 92920 – 92921, 92924 – 92925, 92937, 92938, 92941, 92943, 92944
 
OR –
 
Inpatient or outpatient ICD-9 procedure: 00.66, 36.01, 36.02, 36.03, 36.05, 36.09
 
Stenting:
 
Inpatient CPT-4: 92980, 92981, 92928 – 92929, 92933 – 92934
 
OR –
 
Inpatient or outpatient ICD-9 procedure: 36.06, 36.07
 
CABG:
 
Inpatient CPT-4: 33510 – 33536, 33545, 33572.
 
OR –
 
Inpatient or outpatient ICD-9 procedure: 36.1x, 36.2x
 
Transmyocardial revascularization: Inpatient CPT-4: 33140, 33141 OR - Inpatient ICD-9 procedure: 36.31-36.34
	
Patorno, Elisabetta et al. "Cardiovascular outcomes associated with canagliflozin versus other non-gliflozin antidiabetic drugs: population based cohort study." BMJ 2018;360:k119 http://dx.doi.org/10.1136/bmj.k119
 
Patorno, Elisabetta et al. "Empagliflozin and the Risk of Heart Failure Hospitalization in Routine Clinical Care: A First Analysis from the Empagliflozin Comparative Effectiveness and Safety (EMPRISE) Study." Circulation. 2019 Apr 8. doi: 10.1161/CIRCULATIONAHA.118.039177

	
 
o Chronic heart failure NYHA class II-III
 
o Chronic renal failure: 
 
- eGFR <60 mL/min/1.73m^2 (Modification of Diet in Renal Disease formula)
 
- eGFR <60 mL/min (Cockcroft-Gault formula)
 
 
 
	
Measured 180 days prior to drug initiation in any diagnosis position and inpatient or outpatient care setting
 
414.x, Peripheral vascular disease
 
ICD-9 diagnosis:
 
440.20 – 440.24, 440.29 – 440.32, 440.3, 440.4, 443.9
	
N/A
 
N/A

	
 
o Microalbuminuria or proteinuria
 
o Hypertension and left ventricular hypertrophy by ECG or imaging
 
o Left ventricular systolic or diastolic dysfunction by imaging
 
o Ankle-brachial index <0.9
 
	
Measured 180 days prior to drug initiation in any diagnosis position and inpatient or outpatient care setting
 
428.x, 398.91, 402.01, 402.11, 402.91, 404.01, 404.11, 404.91, 404.03, 404.13, 404.93
	
Measured 180 days prior to drug initiation in any diagnosis position and inpatient or outpatient care setting
 
CKD stage 3-6 585.3x-585.6x

	
 
• No Prior cardiovascular disease: Age ≥ 60 years at screening, AND at least one of the following:
 
	
Age ≥ 60 at drug initiation AND
 
Measured 180 days prior to drug initiation in any diagnosis position and inpatient or outpatient care setting
 
Proteinuria ICD 9 DX 791.0 ICD10 DX R80.X
 
Albumin abnormality ICD9 Dx- 790.99 ICD10 Dx - R77.0
	
3b	
 
o HbA1c ≥ 7.0% at screening
 
	
Measured 180 days prior to drug initiation in any diagnosis position and with 1 inpatient care setting claim AND 2 outpatient care setting claims:
 
Hypertension any ICD-9 code from 401.x – 405.x
	
N/A

	
 
o Ankle-brachial index <0.9
 
	
Measured 180 days prior to drug initiation in any diagnosis position and inpatient or outpatient care setting
 
ICD-9 440.21
	
Measured 180 days prior to drug initiation in any diagnosis position and inpatient or outpatient care setting
 
ICD-9 440.21

	EXCLUSION CRITERIA		
1	Type 1 diabetes	
Measured 180 days prior to drug initiation in any diagnosis position and inpatient or outpatient care setting
 
DM type 1 - At least 1 inpatient or outpatient ICD-9 Dx code of 250.x1 or 250.x3 or ICD-10 Dx code of E10.x in the 6 months prior to drug initiation.
	
Patorno, Elisabetta et al. "Cardiovascular outcomes associated with canagliflozin versus other non-gliflozin antidiabetic drugs: population based cohort study." BMJ 2018;360:k119 http://dx.doi.org/10.1136/bmj.k119
 
Patorno, Elisabetta et al. "Empagliflozin and the Risk of Heart Failure Hospitalization in Routine Clinical Care: A First Analysis from the Empagliflozin Comparative Effectiveness and Safety (EMPRISE) Study." Circulation. 2019 Apr 8. doi: 10.1161/CIRCULATIONAHA.118.039177

2	Use of a GLP-1 receptor agonist (exenatide, liraglutide or other) or pramlintide or any (dipeptidyl peptidase 4 (DPP-4) inhibitor within the 3 months prior to screening	
Dispensing of at least one of the following medications in the 90 days prior to drug initiation:
 
Use of a GLP-1 receptor agonist (exenatide, liraglutide or other) or pramlintide or any (dipeptidyl peptidase 4 (DPP-4) inhibitor within the 3 months prior to index date (Please see AHA therapy sheet.)
	

5	An acute coronary or cerebrovascular event in the previous 14 days	Measured 14 days prior to drug initiation in any diagnosis/procedure position and inpatient care setting MI, stroke, revascularization, PTCA, CABG: Acute MI ICD-9 diagnosis 410.xx Coronary revascularization-PTCA: Inpatient CPT-4: 92973, 92982, 92984, 92995, 92996, 92920 – 92921, 92924 – 92925, 92937, 92938, 92941, 92943, 92944 – OR – Inpatient ICD-9 procedure: 00.66, 36.01, 36.02, 36.03, 36.05, 36.09 Stenting: Inpatient CPT-4: 92980, 92981, 92928 – 92929, 92933 – 92934 – OR – Inpatient ICD-9 procedure: 36.06, 36.07 Transmyocardial revascularization CPT-4: 33140, 33141 – OR – Inpatient ICD-9 procedure: 36.31-36.34 CABG: Inpatient CPT-4: 33510 – 33536, 33545, 33572 – OR – Inpatient ICD-9 procedure: 36.1x, 36.2x Stroke ICD-9 diagnosis: 430.xx Subarachnoid hemorrhage (SAH) 431.xx Intracerebral hemorrhage (ICH) 433.x1 Occlusion and stenosis of precerbral arteries with cerebral infarction 434.x1 Occlusion and stenosis of cerebral arteries with cerebral infarction 436.x Acute, but ill-defined cerebrovascular events	
6	Currently planned coronary, carotid or peripheral artery revascularization	N/A	
7	Chronic heart failure NYHA class IV	Measured 180 days prior to drug initiation in any diagnosis/procedure position and inpatient or outpatient care setting Oxygen use codes: HCPCS: E0424 E0425 E0430 E0431 E0433 E0434 E0435 E0439 E0440 E0441 E0442 E0443 E0444 E0447 E1390 E1391 E1392 E1405 E1406 K0738 S8120 S8121 or ICD-10 : Dependence on Supplemental oxygen Z99.81 ICD-9: Other dependence on machines, supplemental oxygen V46.2	
ORIGINAL DEFINITION: Inpatient Heart failure (CHF) in prior 60 days Any of ICD-9 codes : 428.x, 398.91, 402.01, 402.11, 402.91, 404.01, 404.11, 404.91, 404.03, 404.13, 404.93
 
NEW DEFINITION 4/22/2019: Inpatient diagnosis may not be specific enough for including severe symptomatic class IV patients. Therefore, we decided to incorporate the use of oxygen therapy (not limited to inpatient setting).

8	Current continuous renal replacement therapy	Measured 180 days prior to drug initiation in any procedure position and inpatient or outpatient care setting: ESRD (Please see ESRD codes tab for codes and algorithm used to define ESRD and Renal Transplant)	
Patorno, Elisabetta et al. "Cardiovascular outcomes associated with canagliflozin versus other non-gliflozin antidiabetic drugs: population based cohort study." BMJ 2018;360:k119 http://dx.doi.org/10.1136/bmj.k119
 
Patorno, Elisabetta et al. "Empagliflozin and the Risk of Heart Failure Hospitalization in Routine Clinical Care: A First Analysis from the Empagliflozin Comparative Effectiveness and Safety (EMPIRE) Study." Circulation. 2019 Apr 8. doi: 10.1161/CIRCULATIONAHA.118.039177

9	Estimated glomerular filtration rate (eGFR) (as per MDRD) < 30 mL/min/1.73m  at screening. The criterion is applicable after a target number of 220 subjects with eGFR < 30 mL/min are randomized	N/A	
10	End stage liver disease, defined as the presence of acute or chronic liver disease and recent history of one or more of the following: ascites, encephalopathy, variceal bleeding, bilirubin ≥ 2.0 mg/dL, albumin level ≤ 3.5 g/dL, prothrombin time ≥ 4 seconds prolonged, international normalized ratio (INR) ≥ 1.7 or prior liver transplant	Measured 180 days prior to drug initiation in any diagnosis position and inpatient or outpatient care setting Liver disease- ICD-9 diagnosis: 070.xx, 570.xx- 573.xx 456.0x-456.2x, 576.8x, 782.4x, 789.5x ICD-9 procedure codes: 39.1x, 42.91	
Patorno, Elisabetta et al. "Cardiovascular outcomes associated with canagliflozin versus other non-gliflozin antidiabetic drugs: population based cohort study." BMJ 2018;360:k119 http://dx.doi.org/10.1136/bmj.k119
 
Patorno, Elisabetta et al. "Empagliflozin and the Risk of Heart Failure Hospitalization in Routine Clinical Care: A First Analysis from the Empagliflozin Comparative Effectiveness and Safety (EMPIRE) Study." Circulation. 2019 Apr 8. doi: 10.1161/CIRCULATIONAHA.118.039177

## Appendix A

11	Aprior solid organ transplant or awaiting solid organ transplant	Measured 180 days prior to drug initiation in any diagnosis/procedure position and inpatient or outpatient care setting Please see Organ transplant sheet for ICD-9 Diagnosis codes and ICD-9 and CPT procedure codes.	Patorno, Elisabetta et al. "Cardiovascular outcomes associated with canagliflozin versus other non-gliflozin antidiabetic drugs: population based cohort study." BMJ 2018;360:k119 http://dx.doi.org/10.1136/bmj.k119 Patorno, Elisabetta et al. "Empagliflozin and the Risk of Heart Failure Hospitalization in Routine Clinical Care: A First Analysis from the Empagliflozin Comparative Effectiveness and Safety (EMPRISE) Study." Circulation. 2019 Apr 8. doi: 10.1161/CIRCULATIONAHA.118.039177
12	Malignant neoplasm requiring chemotherapy, surgery, radiation or palliative therapy in the previous 5 years. Subjects with intraepithelial squamous cell carcinoma of the skin (Bowen's disease) treated with topical 5-fluorouracil (5FU) and subjects with basal cell skin cancer are allowed to enter the trial	Measured 180 days prior to drug initiation in any procedure position and inpatient or outpatient care setting History of malignant neoplasm in previous 5 years 140.xx-208.xx (except 173.xx, non-melanoma skin cancer)	Patorno, Elisabetta et al. "Cardiovascular outcomes associated with canagliflozin versus other non-gliflozin antidiabetic drugs: population based cohort study." BMJ 2018;360:k119 http://dx.doi.org/10.1136/bmj.k119 Patorno, Elisabetta et al. "Empagliflozin and the Risk of Heart Failure Hospitalization in Routine Clinical Care: A First Analysis from the Empagliflozin Comparative Effectiveness and Safety (EMPRISE) Study." Circulation. 2019 Apr 8. doi: 10.1161/CIRCULATIONAHA.118.039177
13	Family or personal history of multiple endocrine neoplasia type 2 (MEN2) or familial medullary thyroid carcinoma (FMTC)	Measured 180 days prior to drug initiation in any diagnosis position and inpatient or outpatient care setting ICD-9: MEN Type I: 258.01 MEN Type IIA: 258.02 MEN Type IIB: 258.03 ICD-10: MEN, unspecified: E31.20 MEN, Type I: E31.21 MEN Type IIA: E31.22 MEN, Type IIB: E31.23	
14	Personal history of non-familial medullary thyroid carcinoma	Measured 180 days prior to drug initiation in any diagnosis position and inpatient or outpatient care setting: ICD9: 193 - MALIGNANT NEOPLASM OF THYROID GLAND 194.1 - MALIGNANT NEOPLASM OF PARATHYROID GLAND ICD10: C73	(This is already covered in exclusion criteria #12, but measured and applied again)
15	Any acute condition or exacerbation of chronic condition that would in the Investigator's opinion interfere with the initial trial visit schedule and procedures	N/A	
16	Known or suspected hypersensitivity to trial product(s) or related products	N/A	
17	Known use of non prescribed narcotics or illicit drugs	Measured 180 days prior to drug initiation in any diagnosis position and inpatient or outpatient care setting Drug abuse or dependence ICD-9: 292.xx, 304.xx, 305.2x-305.9x, 648.3x	Patorno, Elisabetta et al. "Cardiovascular outcomes associated with canagliflozin versus other non-gliflozin antidiabetic drugs: population based cohort study." BMJ 2018;360:k119 http://dx.doi.org/10.1136/bmj.k119 Patorno, Elisabetta et al. "Empagliflozin and the Risk of Heart Failure Hospitalization in Routine Clinical Care: A First Analysis from the Empagliflozin Comparative Effectiveness and Safety (EMPRISE) Study." Circulation. 2019 Apr 8. doi: 10.1161/CIRCULATIONAHA.118.039177
18	Simultaneous participation in any other clinical trial of an investigational agent. Participation in a clinical trial with investigational stent(s) is allowed	N/A	
19	Previous participation in this trial. Participation is defined as randomized	N/A	
20	Females of childbearing potential who are pregnant, breast-feeding or intend to become pregnant or are not using adequate contraceptive methods (adequate contraceptive measures as required by local law or practice)	Measured 180 days prior to drug initiation in any diagnosis position and inpatient or outpatient care setting or any drug dispensing prior to drug initiation: i) Encounter for contraceptive management V25 OR Non-oral contraceptives (brand names)- Depo-subQ Provera 104 Depo-Provera, generic Mirena Ortho Evra NuvaRing Implanon Oral contraceptives (generic names)- See "oral contraceptives - generic" sheet. Oral contraceptives (brand names)- See "oral contraceptives iii) plus pregnancy Measured 180 days prior to drug initiation in any diagnosis position and inpatient or outpatient care setting- Refer to Pregnancy Sheet.	Krumme, Alexis A, et. al. "Study protocol for the dabigatran, apixaban, rivaroxaban, edoxaban, warfarin comparative effectiveness research study." J. Comp. Eff. Res. (2018);7(1), 57-66. doi: 10.2217/cer-2017-0053.  We excluded patients using contraceptives because this trial includes non-pregnant women, patients without childbearing potential, and patients who have childbearing potential but are taking precautions such as oral contraceptives (among many other ways) to avoid pregnancy during the trial period. It is impossible to implement such inclusion in real-world data, as childbearing potential is not recorded in claims. In this trials setting, this limitation to implement as an inclusion criteria is due to the following: i) lack of recording of contraceptives and other precautions to avoid pregnancy and ii) patients with diabetes and baseline CV tend to be older and are not likely to be at childbearing age. Therefore, we assumed that patients taking oral contraceptives have childbearing potential, so if they were to stop contraceptive use during follow-up, they could then become pregnant. Also, just to note, this exclusion of contraceptives use excludes very few patients (typically less than 0.1% of patients).
21	Receipt of any investigational medicinal product (IMP) within 30 days prior to this trial.	N/A	

## Appendix A

Trial ID	
Trial Name (with web links)	LEADER
Trial Name (with pdf links)	
NCT	NCT01179048
Trial category	Secondary indication
Therapeutic Area	Endocrinology
RCT Category	4a- Unintended S with label change
Brand Name	
Generic Name	Liraglutide
Sponsor	Novo Nordisk A/S
Year	2016
Measurable endpoint	Composite of Cardiovascular Death, Non-fatal Myocardial Infarction, or Non-fatal Stroke
Exposure	Liraglutide
Comparator	Placebo
Population	
Trial finding	HR = 0.87 (95% CI 0.78-0.97)
Notes	
No. of Patients	
Non-inferiority margin	HR = 1.30
Assay Sens. Endpoint	
Assay Sens. Finding	
Power	90% power to detect non-inferiority
Blinding	
Statistical Method	
Approval indication	

## Appendix A

### **Mortality- Dependent on data source.**

#### 1. All-cause mortality / inpatient mortality

Identified using the vital status file-

Medicare

Identified using the discharge status codes-

Optum-

- 20 = EXPIRED
- 21 = EXPIRED TO BE DEFINED AT STATE LEVEL
- 22 = EXPIRED TO BE DEFINED AT STATE LEVEL
- 23 = EXPIRED TO BE DEFINED AT STATE LEVEL
- 24 = EXPIRED TO BE DEFINED AT STATE LEVEL
- 25 = EXPIRED TO BE DEFINED AT STATE LEVEL
- 26 = EXPIRED TO BE DEFINED AT STATE LEVEL
- 27 = EXPIRED TO BE DEFINED AT STATE LEVEL
- 28 = EXPIRED TO BE DEFINED AT STATE LEVEL
- 29 = EXPIRED TO BE DEFINED AT STATE LEVEL
- 40 = EXPIRED AT HOME (HOSPICE)
- 41 = EXPIRED IN A MEDICAL FACILITY (HOSPICE)
- 42 = EXPIRED - PLACE UNKNOWN (HOSPICE)

Truven-

- 20 - Died
- 22 - Died
- 23 - Died
- 24 - Died
- 25 - Died
- 26 - Died
- 27 - Died
- 28 - Died
- 29 - Died
- 40 - Other died status or Expired at home (Hospice claims only) (depends on year)

## Appendix A

- 41 - Other died status or Expired in medical facility (Hospice claims only) (depends on year)
- 42 - Other died status or Expired - place unknown (Hospice claims only) (depends on year)
- 21 - Died or Disch./Transf. to court/law enforcement (depends on year)

### 2. CV mortality

Information on CV mortality through data linkage with the National Death Index (NDI) will be available for Medicare at a later date. We will conduct secondary analyses using CV mortality at that time.

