### 1.5 Primary trial estimate targeted for replication

HR = 0.87 (95% CI 0.78-0.97) comparing liraglutide to placebo (Marso et al.)

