### 6.3 Outcome variables and study follow-up:

#### 6.3.1 Outcome variables

Effectiveness outcomes of interest (definitions provided in **Appendix A**):

- **Primary outcome:** 3-point major adverse cardiovascular events (MACE), i.e., non-fatal myocardial infarction, non-fatal stroke, or CV mortality
- Secondary outcomes: Individual MACE components:
  - Hospital admission for MI (for purposes of individual component, fatal MI is included)
  - Hospital admission for stroke (for purposes of individual component, fatal stroke is included)
  - All-cause mortality/CV mortality:
    - All-cause inpatient mortality identified using discharge status codes will be used as a proxy for “CV mortality” in commercial databases
    - Information on CV mortality through data linkage with the National Death Index (NDI) will only become available at a later date for Medicare and will be used in secondary analyses.

Control outcomes of interest (control outcomes only serve to assess aspects of study validity but are not further interpreted):

1. For comparison with 2nd Gen. SUs: Severe hypoglycemia (we expect to see protective effect; American Diabetes Association, 2018)

- A dosage change on the index treatment does not fulfill this criterion
- An added treatment that is not part of the exposure or comparator group does not fulfill this criterion (e.g. if a liraglutide user adds insulin, he or she does not get censored at the time of insulin augmentation)

For the ITT analyses, the censoring based on the augmentation/switching and treatment discontinuation will be replaced with a maximum allowed follow-up time of 365 days.

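### The primary 3-point MACE is labelled with CV mortality but counts deaths from any cause, and no combined MI-or-stroke estimate is planned that leaves the death proxy out

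*Combined protocol and SAP*

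**What the plan says.** The endpoint to be replicated is given in Section 1.3 and on the Appendix A trial summary sheet: "Composite of Cardiovascular Death, Non-fatal Myocardial Infarction, or Non-fatal Stroke". Section 1.5 gives the target: "HR = 0.87 (95% CI 0.78-0.97) comparing liraglutide to placebo".

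Section 6.3.1 describes the primary 3-point MACE in the same terms: "i.e., non-fatal myocardial infarction, non-fatal stroke, or CV mortality". The operational definitions differ from that label:

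- For the commercial databases, Section 6.3.1 states: "All-cause inpatient mortality identified using discharge status codes will be used as a proxy for" CV mortality.
- For Medicare, the Appendix A Mortality sheet says of all-cause mortality: "Identified using the vital status file".
- The Appendix A row for the primary outcome writes "Inpatient mortality/MI/Stroke" without separating the databases, and refers to the Mortality sheet.
- CV death from the National Death Index (NDI) "will only become available at a later date for Medicare and will be used in secondary analyses" (Section 6.3.1). The Mortality sheet repeats this: "We will conduct secondary analyses using CV mortality at that time". No such linkage is described for Optum or MarketScan.

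MI, stroke and mortality are also listed as individual secondary outcomes, and Section 14.1 asks for results by endpoint and by comparator. A combined MI-or-stroke outcome is not listed.

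**The concern.** The label and the coded endpoint differ in cause of death. LEADER's 0.87 is for a composite with CV death. The planned primary composite also counts non-CV deaths, and the Section 10 power tables apply 0.87 to it unchanged.

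This matters more because deaths are uneven after matching. The reasons-for-censoring tables in Section 9 show 827 DPP4i against 444 liraglutide deaths with 84,345 patients per arm, and 595 against 263 with 54,182 per arm for sulfonylureas. The death component may therefore carry much of any departure of the composite from 1. The plan offers MI alone and stroke alone as estimates free of the proxy, each with fewer events than the two combined.

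**Working it through.** **Inputs.** Matched numbers, risks per 1,000 and expected events are from Sections 9 and 10. Deaths by arm are from the Section 9 censoring tables. Follow-up medians are from Section 9.

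**1. The plan's own figure.** Events = 2 × matched patients per arm × risk. Pooled DPP4i: 2 × 84,345 × 0.02167 = 3,655.5, as stated. Power = Φ(√(events/4) × |ln 0.87| − 1.96) = 0.988, also as stated.

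The pooled risk of 21.67 is the unweighted mean of 14.30, 12.11 and 38.60. Summing the three databases instead gives 548.7 + 503.2 + 3,426.2 = 4,478.2 events. The sulfonylurea sum is 464.9 + 612.7 + 2,765.2 = 3,842.8, against 3,261.8 stated. I use the sums as the main case.

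**2. Upper bound on the death share.** DPP4i: (827 + 444)/4,478 = 28%. Sulfonylurea: (595 + 263)/3,843 = 22%. These are upper bounds because some deaths follow an MI or stroke and are then not first events.

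**3. Person-time ratio r (liraglutide/referent).** Person-time is not given, so ratios of medians stand in for it.
- DPP4i: 148/173 = 0.86 (Optum) and 159/209 = 0.76 (MarketScan and Medicare).
- Sulfonylurea: 148/181 = 0.82 and 148/231 = 0.64.

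The Medicare arm rows repeat the MarketScan rows exactly, so the Medicare ratio is uncertain.

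**4. Composite with no MI/stroke effect.** Let f be the share of deaths that are first events, E the expected events and D the total deaths. Then M = E − f × D is the number of MI/stroke events. With an MI/stroke rate ratio of 1 they split as M/(1+r) in the referent arm and M × r/(1+r) in the liraglutide arm. The composite rate ratio is

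[(M × r/(1+r) + f × liraglutide deaths)/r] ÷ [M/(1+r) + f × referent deaths].

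Example, DPP4i, f = 1, r = 159/209: M = 3,207, split 1,821 and 1,386. The ratio is [(1,386 + 444)/0.761]/(1,821 + 827) = 0.908.

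| Comparison | Events | r | f = 100% | f = 80% | f = 60% |
|---|---|---|---|---|---|
| DPP4i | 4,478 | 0.86 to 0.76 | 0.88-0.91 | 0.90-0.93 | 0.93-0.94 |
| DPP4i | 3,656 (stated) | 0.86 to 0.76 | 0.85-0.89 | 0.88-0.91 | 0.91-0.93 |
| Sulfonylurea | 3,843 | 0.82 to 0.64 | 0.88-0.92 | 0.90-0.94 | 0.93-0.95 |

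Every value lies inside 0.78-0.97. The choices of f are assumptions.

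**5. Events and power for MI or stroke combined, DPP4i.** At least 3,656 − 1,271 = 2,385 or 4,478 − 1,271 = 3,207 events. At an assumed HR of 0.87, power is 0.93 or 0.98. If MI and stroke each took half of these events (an assumption), each alone would have power of about 0.67 to 0.80.

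**The case against.** **The calculation does not isolate cause of death.** It uses total deaths. If all 1,271 were true CV deaths, the composite would be the same. A reader might infer that any-cause counting as such produces a LEADER-like result, or that non-CV deaths explain the imbalance. The documents give no CV/non-CV split and support neither inference. Some of these deaths may reflect a real CV effect. Measured covariates are balanced after DPP4i matching (Medicare comorbidity index 2.88 in both arms), so residual confounding is possible but not shown. This objection stands.

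**The result does not hit 0.87.** Lower values come from assuming equal follow-up (0.84 on 4,478 events), which conflicts with the shorter liraglutide follow-up in Section 9, or from the 3,656 events built on an unweighted mean risk. On 4,478 events and the follow-up ratios the value is 0.88-0.91 at most strength. No section makes LEADER's interval the rule for agreement. This also stands: the claim is only that the value can fall inside that interval.

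**The sources may not match.** The death row is a censoring reason in the dummy-outcome run of November 2019. The report links below the risk table are dated April 2019. If the Medicare endpoint is inpatient death, as the Appendix A outcome row could be read, the death row may include deaths outside it.

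**Components are already reported.** MI, stroke and mortality appear separately, so a composite driven by deaths would be visible. That is true and lowers the stakes. What remains is that MI alone and stroke alone are each weaker, and nothing combines them without the proxy.

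**Conclusion.** The mismatch between label and coded endpoint is documented. The plan discloses the proxy, so nothing is concealed. If MI and stroke were unaffected, the death component alone could put the DPP4i composite at about 0.88-0.91 with every death a first event, or about 0.93-0.94 with 60%. The sulfonylurea comparison behaves alike, so the point does not depend on which comparator is primary (Sections 5.1 and 13.1 differ on this).

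These values rest on three quantities that the documents do not give: the first-event share, person-time, and whether the tabulated deaths are those in the outcome. The stronger reading, that the primary analysis will reproduce 0.87 through non-CV deaths, is not supported. Deaths as a quarter or more of composite events is likewise a ceiling, not an established share. The point justifies a cheap improvement and does not invalidate the design.

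**What to change.** In Sections 6.3.1 and 14.1, pre-specify a 2-point composite, first hospitalised MI or stroke, as a secondary or sensitivity outcome. Analyse it like the primary outcome for each comparator, and print its HR beside the 3-point HR and the mortality HR already planned. Label the current primary as death from any cause (proxy for CV death), MI or stroke. Section 13 is still undated, so this can be settled before comparative results exist.

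The cost is one more Cox model per comparator on events already coded, plus wording. The 2-point composite has fewer events: at least 2,385 to 3,207 for DPP4i, with power of about 0.93 to 0.98 if 0.87 is assumed. That HR is borrowed, since the documents give no LEADER 2-point HR.

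Two further steps are not recommended. Requiring the 2-point composite to agree before claiming replication would reject a true effect confined to CV death, and has no documented benchmark. Making the NDI-based Medicare analysis the only comparison with 0.87 would drop Optum and MarketScan from it and wait for data with no stated date.
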